2.2. Endpoints

Primary endpoint:

- Monocular distance (4 m) logMAR visual acuity under bright lighting conditions with a high luminance, high contrast chart (bright HLHC), measured per [REDACTED]

Monocular distance logMAR visual acuity under bright HLHC conditions will be collected post-lens fitting for each subject eye using the Precision Vision 4-meter high contrast ETDRS charts. One measurement per eye (OD and OS) will be collected. See Sections 7.2 and Appendix D for details regarding primary endpoint data collection.

Secondary endpoints:

- Lens fit acceptance, measured per [REDACTED]

Lens fit acceptance will be assessed post lens fitting for each subject eye. Acceptable fit is a binary response where Y=1 if lens fit is deemed acceptable by the investigator and Y=0 otherwise. An unacceptable fit is deemed by one of the following criteria:

- limbal exposure at primary gaze or with extreme eye movement;
- edge lift;
- excessive movement in primary and up gaze; or
- insufficient movement in all three of the following conditions: primary gaze, up gaze, and Josephson push up.

See Sections 7.2 and Appendix D for details regarding secondary endpoint data collection.

Clinical Study Protocol

Johnson & Johnson Vision Care, Inc.

Other endpoints:

- Monocular distance (4 m) logMAR visual acuity under dim lighting conditions with a low luminance, high contrast chart (dim LLHC), measured per [REDACTED]
[REDACTED]
- Monocular distance (4 m) logMAR visual acuity under bright lighting conditions with a high luminance, low contrast chart (bright HLLC), measured per [REDACTED]
[REDACTED]
- Lens centration and movement characteristics, measured per [REDACTED]
- Slit lamp findings, measured per [REDACTED]
- Subject reported ocular symptoms, measured per [REDACTED]
- Pupil diameter (mm), measured per [REDACTED]

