Both EMO-200 and EMO-118 lenses have the same optical design intended for myopia control in pediatric populations. They have the same diameter and base cure and are made in the same material. The EMO-200 lens is manufactured in Ireland for supporting commercialization. It is considered a “re-design” of the EMO-118 lens driven by upgrades to the lens design system to enable metrology of the complex optics on the lens plastic molds. Comparing lenses made under the code name of EMO-200 with those made under the code name of EMO-118, thorough assessments from aspects of lens design, product specifications, test methods, raw materials, and manufacturing process, suggest no reason to believe that the clinical performance of the two lenses would be different. The effectiveness of the optical design in myopia correction and slowing axial elongation and refraction change of the eye has been demonstrated in [REDACTED] with the EMO-118 lens. Any deviation in the EMO-200 lens from the intended optical and/or mechanical designs, which may lead to the lens potentially being less effective, will be manifested as differences in the lens visual performance and or fit performance, compared to the EMO-118 lens. As such, monocular distance visual acuity and lens fit acceptance of the EMO-200 lens are selected to be the primary and secondary endpoints of this investigation as surrogates in place of assessment of the lens long-term myopia control effect. In addition, subject reported ocular symptoms with the study lenses will be collected.

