1.12	Eligibility Following Baseline Evaluation	
All responses to Inclusion Criteria questions must be answered “yes” and all responses to Exclusion Criteria questions must be answered “no” for the subject to be considered eligible.
 
Note: If subject is deemed to be ineligible after baseline, proceed to Final Evaluation and complete Subject Disposition. Refraction and Biomicroscopy forms do not need to be completed as part of Final Evaluation.
	[REDACTED]

Visit 1: Treatment 1 Lens Fitting			
Step	Procedure	Details	[REDACTED]
1.13	Lens Selection	
Assign the study lens based on the lens fitting schedule. Record the randomization ID.
 
Select the contact lens power based on subjective best sphere refraction.
	[REDACTED]
1.14	Lens Insertion	
The investigator or the subject inserts the study lenses. Record the time of lens insertion.
 
Check for lens damage under the slit lamp before proceeding with lens settling.
 
Replace damaged lenses if applicable.
 
Ensure the subject is given a Patient Instruction Guide.
	[REDACTED]

Clinical Study Protocol
Johnson & Johnson Vision Care, Inc.

Visit 1: Treatment 1 Lens Fitting			
Step	Procedure	Details	
1.15	Lens Settling	Allow the study lenses to settle for a minimum of 10 minutes.	
1.16	Subjective Lens Fit Assessment	
Evaluate overall lens fit acceptance (acceptable or unacceptable) based on centration, movement and other fitting characteristics.
 
An unacceptable fit is deemed by one of the following criteria:
 
 • limbal exposure at primary gaze or with extreme eye movement; • edge lift; • excessive movement in primary and up gaze; or • insufficient movement in all three of the following conditions: primary gaze, up gaze, and Josephson push up. 
Note: if lens fit is unacceptable, the subject will skip Steps 1.17 to 1.22, and proceed with Step 1.23 and Treatment 2 Lens Fitting. The subject will be discontinued after Subjective Lens Fit Assessment for the Treatment 2 has been completed.
	
1.17	Over the Lens Distance Snellen VA	Record the subject's distance visual acuity to the nearest letter with the study lenses (OD, OS).	

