1.20	Distance ETDRS LogMAR Visual Acuity	Perform monocular distance ETDRS LogMAR visual acuity test at a 4-meter distance with the subject wearing the study lenses under the following conditions:	

Clinical Study Protocol
Johnson & Johnson Vision Care, Inc.

Visit 1: Treatment 1 Lens Fitting			
Step	Procedure	Details	
		
 1. dim illumination (1.4-1.6 lux, or -0.8--0.6 EV), low luminance (2.5-2.8 cd/m², or 4.3-4.5 EV), with high contrast charts (LLHC); 2. bright illumination (686-788 lux, or 8.1-8.3 EV), high luminance (181-208 cd/m², or 10.5-10.7 EV) with low contrast charts (HLLC); 3. bright illumination (686-788 lux, or 8.1-8.3 EV), high luminance (181-208 cd/m², or 10.5-10.7 EV) with high contrast charts (HLHC); 
The Precision Vision 4-meter high (Charts 1 – 4) and low contrast (Chart 1 and 2) ETDRS charts will be used.
 
One measurement per condition for OD and OS, respectively.
	
1.21	Visual Experience	Encourage the subjects to look at objects at distant and near, and if possible, under bright and dim lighting conditions.	
1.22	Subject Reported Ocular Symptoms	Subjects will respond to a verbal open-ended symptoms questionnaire regarding the study lens.	
1.23	Study Contact Lens removal	Subjects remove and discard the study contact lenses.	

Visit 1: Treatment 2 Lens Fitting

Allow 15 minutes of washout period with the subjects wearing their habitual correction before proceeding to Treatment 2 Lens Fitting. If the subject wears habitual soft contact lens to the visit, instruct the subject to remove own lenses and store them temporarily in a lens case (provided by the investigator) with saline before continuing with Treatment 2 Lens Fitting.

Repeat all steps under Treatment 1 Lens Fitting for the second trial lens, per the randomization scheme.

FINAL EVALUATION

The final evaluation will take place immediately following the completion of Visit 1 per the study protocol. It may also take place at any point the subject discontinues the study or is terminated from the study.

Clinical Study Protocol

Johnson & Johnson Vision Care, Inc.

In the event of an adverse event, Final Evaluation will be performed after all required follow-up of the adverse event is complete (see Section 13.3 for detailed instructions on follow-up of adverse events).

Final Evaluation			
Step	Procedure	Details	

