14.7. Other Analyses

Summary statistical analysis will be provided for the following other observations:

Other endpoints:

- Monocular distance (4 m) logMAR visual acuity under dim lighting conditions with a low luminance, high contrast chart (dim LLHC), measured per [REDACTED]
[REDACTED]
- Monocular distance (4 m) logMAR visual acuity under bright lighting conditions with a high luminance, low contrast chart (bright HLLC), measured per [REDACTED]
[REDACTED]

Clinical Study Protocol

Johnson & Johnson Vision Care, Inc.

- Lens centration and movement characteristics, measured per [REDACTED]
- Slit lamp findings, measured per [REDACTED]
- Subject reported ocular symptoms, measured per [REDACTED]
- Pupil diameter (mm)

Further exploratory analysis will be considered if necessary, at discretion of the Study Responsible Clinician.

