14.9. Procedure for Handling Missing Data and Drop-Outs

Missing or spurious values will not be imputed. The count of missing values will be included in the summary tables and listings.

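### The Step 1.16 skip rule leaves no ocular-symptom record for any lens wear judged an unacceptable fit, so the symptom summary by lens is conditional on acceptable fit

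*Combined protocol and SAP*

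**What the plan says.** The note to Step 1.16 (Section 7.2, Treatment 1 Lens Fitting) reads: "if lens fit is unacceptable, the subject will skip Steps 1.17 to 1.22, and proceed with Step 1.23 and Treatment 2 Lens Fitting". Its next sentence adds: "The subject will be discontinued after Subjective Lens Fit Assessment for the Treatment 2 has been completed". Step 1.22, which closes the skipped block, is the symptom question: "Subjects will respond to a verbal open-ended symptoms questionnaire regarding the study lens". Step 1.23 is lens removal. The second lens follows the same route: "Repeat all steps under Treatment 1 Lens Fitting for the second trial lens, per the randomization scheme".

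Elsewhere the protocol treats symptoms as data to be gathered on the lenses generally:

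- Section 4.2: "In addition, subject reported ocular symptoms with the study lenses will be collected". It states no exception for a failed fit.
- Section 2.2 lists symptoms among the other endpoints, and Section 14.7 includes them where it says "Summary statistical analysis will be provided for the following other observations".
- Section 14.3 gives ocular symptom as an example of a safety endpoint when it defines the Safety Population.
- Section 8.2 tells the investigator to finish the visit in progress when a subject is discontinued.
- Section 14.9: "Missing or spurious values will not be imputed". It goes on to say that missing values will be counted in tables and listings.

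**The concern.** Whether a child is asked about a lens depends on how that lens fitted, and fit acceptance is the secondary endpoint. A lens showing edge lift, limbal exposure or excessive movement may well be the one that draws a complaint, and it is the one not asked about. The symptom table would then describe acceptable fits only, although its title and Section 4.2 suggest that it describes the lenses. If one lens fitted worse than the other, its symptomatic wears could drop out more often and the two lenses could look alike.

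No other record fills the gap. The exit slit lamp examination (Final Evaluation, F.3) comes after both lenses have been worn, so a finding cannot be assigned to one of them. The adverse event documentation in Section 13.3 asks for a diagnosis rather than a symptom. Section 1.4 promises attention to visual complaints during fitting, but no step other than 1.22 records them by lens.

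**Working it through.** The plan gives no symptom rate and no expected number of lost answers, so there is no figure of its own to reproduce. Table 7 is not in dispute.

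**Which wears have a symptom record under Step 1.16**

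| First lens | Second lens | Symptom record |
|---|---|---|
| acceptable | acceptable | both lenses |
| acceptable | unacceptable | first lens only |
| unacceptable | acceptable | neither lens |
| unacceptable | unacceptable | neither lens |

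The third row shows that the loss is not confined to poor fits.

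**Inputs from Section 14.2.** Acceptance per eye p = 0.95; correlation between eyes 0.80; correlation across periods 0.50; 56 completers and 67 enrolled.

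**Assumptions of this check.** A wear counts as unacceptable if at least one eye fails. The 0.50 is applied to that subject-level result. The two sequences are equally frequent.

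**Unacceptable wears per lens.** q = 1 − [p² + 0.80·p(1−p)]

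- p = 0.95: 1 − [0.9025 + 0.80 × 0.0475] = 0.0595, which is 3.3 of 56 or 4.0 of 67.
- p = 0.90: 1 − [0.81 + 0.80 × 0.09] = 0.118, which is 6.6 of 56.
- p = 0.85: 1 − [0.7225 + 0.80 × 0.1275] = 0.1755, which is 9.8 of 56.

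If the note is read as needing both eyes to fail, p = 0.95 gives 0.05² + 0.80 × 0.0475 = 0.0405, or 2.3 of 56.

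**Good-fit second wears also lost, 95% for both lenses**

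- P(both lenses fail) = q² + 0.50·q(1−q) = 0.0035 + 0.0280 = 0.0315.
- P(first fails, second acceptable) = 0.0595 − 0.0315 = 0.0280, which is about 1.6 of 56 subjects.
- Total: 2 × 3.3 + 1.6 = about 8.2 of the 112 wears of 56 subjects.

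**Effect on the comparison.** Let g and b be the symptom rates with acceptable and unacceptable fit, the same for both lenses. The true difference is (q_T − q_C)(b − g). The recorded difference is g − g = 0, because only acceptable fits contribute. The documents give neither rate. As an illustration, assume g = 10% and b between 30% and 80%.

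| Acceptance, worse v better lens | True excess for the worse lens | Recorded |
|---|---|---|
| 95% v 95% | 0 | 0 |
| 90% v 95% | 0.0585 × 0.20 to 0.0585 × 0.70 = 1.2 to 4.1 points | 0 |
| 85% v 95% | 0.116 × 0.20 to 0.116 × 0.70 = 2.3 to 8.1 points | 0 |

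If b = g, or if no fit is unacceptable, the difference is zero in every row.

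**The case against.** The case for leaving the rule alone has several parts.

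- **Visibility.** Section 14.9 has missing values counted in the tables, and each unacceptable fit counts against its lens in the secondary endpoint, analysed in the Safety Population (Section 14.6). A reader would see missing symptom counts beside the fit failures. This stands: the gap would be visible, although the answers themselves could not be recovered.
- **Rarity.** Section 14.2 reports no unacceptable fit in the historical study, calls 95% the worst case, and assumes no difference between the lenses. On those figures the loss is small or nil and the bias between lenses is zero. This also stands.
- **The 85% scenario.** It lies at the non-inferiority margin if the Control is at 95%. There the fit test should usually fail, and Section 2.3 requires both hypotheses to be met. A favourable symptom table would not rescue the Test lens.
- **Comparability.** A child asked straight after Step 1.16 has had no over-refraction, power modification or visual-experience step. Blur in particular would not be comparable with answers from the full sequence. This is fair, and is a reason to report by fit status rather than only pooled.
- **Unseen text.** Section 14 defers detail to a stand-alone SAP, and the symptom procedure in Appendix D is redacted. Either might govern reporting, but neither could restore an answer that Step 1.16 tells the site not to collect.

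A reader might infer that the symptom data are biased towards the worse-fitting lens as a matter of fact, or that exactly the poor fits are lost. The documents support neither. The direction needs both a fit difference and more symptoms with poor fit, and some acceptable second wears are lost too.

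**Conclusion.** The point holds as a gap in data collection. Every wear judged unacceptable, and every acceptable second wear after a failed first lens, has no symptom record. The symptom summary is therefore conditional on acceptable fit, contrary to Section 4.2 and in tension with Section 8.2.

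The expected loss runs from nothing, at the historical rate, to about 3 of 56 (or 4 of 67) subjects per lens plus about 1.6 good-fit second wears per 56, at the plan's 95%. The 56 is the completer target, and children with a failed fit do not complete. The proper base is the number fitted, which at the planned enrolment cannot exceed about 67.

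A distorted comparison between lenses is possible but not shown. It rests on an assumed link between poor fit and symptoms and on unequal acceptance. It would also be tempting to read this as a threat to the non-inferiority conclusions. It is not one: symptoms are descriptive, no hypothesis uses them, and the fit result is recorded before the skip. The change is worth making because it is cheap and because a failed fit is where a symptom answer is informative.

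**What to change.** Reword the Step 1.16 note so that after an unacceptable fit only Steps 1.17 to 1.21 are skipped and Step 1.22 is completed before lens removal at Step 1.23. Apply this in both treatments, so that a child due to be discontinued after the second fit assessment is also asked about the second lens before it comes out. The discontinuation rule itself stays as written, and Step 1.16 must be reconciled with Sections 4.2 and 8.2.

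In Section 14.7, summarise symptoms by lens, split by fit accepted yes or no. Add a note that answers after an unacceptable fit come without power modification or the visual-experience step, and give missing counts by lens and reason.

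The cost is one line in the protocol, the matching eCRF skip logic, and one short verbal question for a few children. It needs no new staff, visit or instrument. If collection is not changed, the least that should be done is to label the symptom tables as conditional on acceptable fit and to give those missing counts.

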7.3. Unscheduled Visits

If, during the investigation, a subject requires an unscheduled visit to the clinical site, the following information will be collected, as appropriate:

- Chief complaint prompting the visit. If the reason is an adverse event, the applicable eCRF for the adverse event must be completed and subject record completed as appropriate.
- Date and time of the visit and all procedures completed at the unscheduled visit.
- Review of adverse event and concomitant medications.
- Documentation of any test article dispensed or collected from the subject, if applicable.
- Slit lamp findings (using the Slit Lamp Classification Scale).

If the Investigator withdraws a subject from the study, the final study visit case report forms must be completed indicating the reason(s) why the subject was withdrawn. The subject record must be completed documenting the date and primary reason for withdrawal and the study CRA notified.

Clinical Study Protocol

Johnson & Johnson Vision Care, Inc.

Any ocular and non-ocular Adverse Events that are ongoing at the time of the study visit will be followed by the Investigator, within licensure, until they have resolved, returned to pre-treatment status, stabilized, or been satisfactorily explained. If further treatment i.e., beyond licensure is required, the subject will be referred to the appropriate health care provider.

The following information will be collected during an unscheduled visit.

Unscheduled Visit			
Step	Procedure	Details	
U.1	Reason for unscheduled visit	Specify the reason for the visit.	
U.2	Chief Complaints	Record the subject's chief complaints for reasons for the unscheduled visit.	
U.3	Adverse Events and Concomitant Medications Review	Review any changes to the subject's medical history or concomitant medications from the previous study visit. Record any changes, and any adverse events.	
U.4	Entrance VA	Record the entrance distance visual acuity (OD, OS) to the nearest letter.	
U.5	Subjective Sphero-cylindrical Refraction	Perform bare-eye subjective sphero-cylindrical refraction with a phoropter and record the best-corrected distance visual acuity (OD and OS) to the nearest letter.	
U.6	Slit Lamp Biomicroscopy	Slit Lamp Classification Scale per ISO 11980 will be used to grade the findings. If the clearance of the fluorescein needs to be expedited, preservative-free rewetting drops or saline may be instilled.	
U.7	Exit Visual Acuity	Record the subject's exit distance visual acuity (OD, OS) to the nearest letter.	

7.4. Laboratory Procedures

Not Applicable.

8. SUBJECTS COMPLETION/WITHDRAWAL

8.1. Completion Criteria

Subjects are considered to have completed the study if they:

- provided informed consent;
- are eligible;
- completed the study visit.

Clinical Study Protocol

Johnson & Johnson Vision Care, Inc.

8.2. Withdrawal/Discontinuation from the Study

A subject will be withdrawn from the study for any of the following reasons:

- Subject withdrawal of consent.
- Subject not compliant to protocol (e.g., refusing any protocol specified procedure)
- Subject no longer meets eligibility criteria (e.g. the subject becomes pregnant).
- Subject develops significant or serious adverse events, and unable to complete the scheduled visit.
- Subjects who have experienced a Corneal Infiltrative Event (CIE).
- Investigator's clinical judgment regarding the subject safety reasons (that it is in the best interest of the subject to stop treatment).

For discontinued subjects, the Investigator will:

- Complete the current visit (scheduled or unscheduled).
- Complete the Final Evaluation, indicating the reason that the subject was discontinued from the study.
- Record the spherocylindrical refraction with best corrected distance visual acuity.
- Collect used test article(s) (worn during the visit) from the subject and discard them, unless otherwise stated in section 7.2.
- Make arrangements for subject care, if needed, due to their study participation

Additional subjects will be enrolled if a subject discontinues from the study prematurely.

In cases where a subject is lost to follow-up, every possible effort must be made to contact the subject and determine the reason for discontinuation/withdrawal. The measures taken to follow up must be documented including two written attempts and a certified letter (or equivalent) as the final attempt.

9. PRE-STUDY AND CONCOMITANT INTERVENTION/MEDICATION

Concomitant medications will be documented during screening and updated during the study.

Disallowed medications for this study include:

Any medication and therapies that would normally contraindicate contact lens wear or have ocular side effects that would affect vision assessment.

Concomitant therapies that are disallowed include:

1. Contact lens corneal reshaping/CRT/orthokeratology
2. Any vision training/vision therapy/orthoptics/patching
3. Any therapies that the investigator feels would be contraindicated in contact lens wear or would affect vision assessment.

Clinical Study Protocol

Johnson & Johnson Vision Care, Inc.

9.1. Systemic Medications

Certain systemic medications are known to have a higher likelihood to interfere with contact lens wear, chiefly by disrupting the tear film.

A summary of disallowed systemic medications that are typically disallowed in a contact lens research is shown in Table 4. This is especially relevant to subjects with a history of taking medications listed in Table 4 on a long-term, routine basis, but have only used these medications for less than 6 months. However, because this is a one-visit, non-dispensing study, and the subject will only wear the study lenses for up to 4 hours in the investigator's office, subjects with a history of taking these medications will be allowed to enroll only if:

- The medications have been taken on a continual, routine basis for at least 6 months (2 weeks for antihistamines), and
- The subject has demonstrated successful contact lens wear while taking the medication.

Or:

- The subject was taking the medication on a temporary basis and ceased taking that medication at least 2 weeks prior to signing the informed consent (this is considered sufficient time for the medication to have left the body prior to enrollment).

Or:

- The subject is a neophyte. Based on the investigator's assessment, the use of these medications will not interfere with the subject's participation in the study or with the assessment of vision and lens fit.

Table 4: Potential Disallowed Systemic Medications

Class of Drug	Common Indication(s)	Common Examples
Estrogens (not including contraceptive medication)	Menopause, osteoporosis, vaginitis	Vagifem, Estrace, Climara, Vivelle-Dot, Premarin, Minivelle, etc.
Antihistamines	Allergic rhinitis, sedation, hives, allergic conjunctivitis, skin allergy, itching, motion sickness	Hydroxyzine, Promethagan, Phenadoz, Vistaril, Claritin, Zyrtec, Astepro, Astelin, Optivar, Allegra, Benedryl, etc.
Anticholinergics	Irritable bowel syndrome, Parkinson's disease, peptic ulcer, cystitis, nasal congestion, cold symptoms, overactive bladder, COPD	Bentyl, Spiriva, Atrovent, Hyosyne, Levsin, Symax Fastab, Symax SL, Homax SL, Cogentin, Transderm Scop, etc.
Beta-blockers	Hypertension, angina, heart attack, migraine, atrial fibrillation, adrenal cancer, essential tumor, glaucoma	Toprol XL, Lopressor, Tenormin, Propranolol, Timoptic, Trandate, Inderal LA, etc.

Clinical Study Protocol
Johnson & Johnson Vision Care, Inc.

Class of Drug	Common Indication(s)	Common Examples
Psychotropics	Antipsychotic (schizophrenia, mania), antidepression, antiobsessive, antianxiety, mood stabilizer, stimulants (ADHD)	Zoloft, Celexa, Prozac, Lexapro, Effexor, Cymbalta, Ativan, Xanax, Desyrel, Wellbutrin, etc.
Vitamin A analogs	Cystic acne	Isotretinoin
Human growth hormone products	Short stature of unknown cause as well as poor growth due to a number of medical causes	Genotropin, Nutropin, Saizen, etc.

